5.7 Criteria for Taking a Participant Off Study

Participants will be removed from study when any of the following criteria apply:

- Lost to follow-up
- Withdrawal of consent for data submission
- Death
- Completion of required 3 years follow-up

The reason for taking a participant off study, and the date the participant was removed, must be documented in the case report form (CRF).

The research team will update the relevant Off Study information in OnCore.

6. DOSING DELAYS/DOSE MODIFICATIONS

Dose delays will be made as indicated in the following tables. The descriptions and grading scales found in the revised NCI Common Terminology Criteria for Adverse Events (CTCAE) version 4.0 will be utilized for dose delays and dose modifications. A copy of the CTCAE version 4.0 can be downloaded from the CTEP website http://ctep.cancer.gov/protocolDevelopment/electronic_applications/ctc.htm.

6.1 Toxicity Management

Table 4: Gastrointestinal Adverse Event Management

Note: Rule out non-inflammatory causes. If non-inflammatory cause is identified, treat accordingly and continue protocol therapy. Opiates/narcotics may mask symptoms of perforation. Infliximab should not be used in cases of perforation or sepsis.		
Grade of Diarrhea / Colitis	Management	Follow-Up
Grade 1	Continue protocol therapy. Treat symptoms as clinically appropriate.	Monitor patient closely for worsening symptoms. Educate patient to report worsening immediately. If worsens: Treat as Grade 2 or \geq Grade 3.
Grade 2	Delay protocol therapy. Treat symptoms as clinically appropriate.	If improves to Grade 1: Resume protocol therapy If persists > 5-7 days or recurs: Administer 0.5-1.0 mg/kg/day methylprednisolone or oral equivalent When symptoms improve to Grade 1, taper steroids over at least 1 month, consider prophylactic antibiotics for opportunistic infections, and resume therapy per protocol. If worsens or persists > 3-5 days with oral steroids: Treat as \geq Grade 3.

Table 4: Gastrointestinal Adverse Event Management

Note: Rule out non-inflammatory causes. If non-inflammatory cause is identified, treat accordingly and continue protocol therapy. Opiates/narcotics may mask symptoms of perforation. Infliximab should not be used in cases of perforation or sepsis.

Grade of Diarrhea / Colitis	Management	Follow-Up
≥ Grade 3	
Permanently discontinue protocol therapy
 
Administer 1.0 to 2.0 mg/kg/day methylprednisolone IV or IV equivalent
 
Add prophylactic antibiotics for opportunistic infections
 
Consider lower endoscopy as clinically appropriate
	
If improves:
 
Continue steroids until grade 1, then taper over at least 1 month
 
If persists > 3-5 days, or recurs after improvement:
 
Add infliximab 5 mg/kg (if no contraindication)
 
Note: Infliximab should not be used in cases of perforation or sepsis

Patients on IV steroids may be switched to an equivalent dose of oral corticosteroids (e.g. prednisone) at start of tapering or earlier, once sustained clinical improvement is observed. Lower bioavailability of oral corticosteroids should be taken into account when switching to the equivalent dose of oral corticosteroids.

Table 5: Renal Adverse Event Management

Note: Rule out non-inflammatory causes. If non-inflammatory cause, treat accordingly and continue protocol therapy.

Grade of Creatinine Elevation	Management	Follow-Up
Grade 1	
Continue protocol therapy.
 
Monitor creatinine weekly.
	
If returns to baseline:
 
Resume routine creatinine monitoring per protocol
 
If worsens:
 
Treat as Grade 2-3 or 4

Table 5: Renal Adverse Event Management

Note: Rule out non-inflammatory causes. If non-inflammatory cause, treat accordingly and continue protocol therapy.

Grade of Creatinine Elevation	Management	Follow-Up
Grade 2 – 3	
Delay protocol therapy
 
Monitor creatinine every 2-3 days
 
Administer 0.5 to 1.0 mg/kg/day methylprednisolone IV or oral equivalent
 
Consider renal biopsy with nephrology consult as clinically appropriate
	
If returns to Grade 1:
 
Taper steroids over at least 1 month, consider prophylactic antibiotics for opportunistic infections, and resume protocol therapy and routine creatinine monitoring per protocol
 
If elevations persist > 7 days or worsens:
 
Treat as Grade 4

Grade 4	
Permanently discontinue protocol therapy
 
Monitor creatinine daily
 
Administer 1.0-2.0 mg/kg/day methylprednisolone IV or IV equivalent
 
Consult nephrologist and consider renal biopsy as clinically appropriate
	
If returns to Grade 1:
 
Taper steroids over at least 1 month and add prophylactic antibiotics for opportunistic infections

Patients on IV steroids may be switched to an equivalent dose of oral corticosteroids (e.g. prednisone) at start of tapering or earlier, once sustained clinical improvement is observed. Lower bioavailability of oral corticosteroids should be taken into account when switching to the equivalent dose of oral corticosteroids.
		

Table 6: Pulmonary Adverse Event Management

Note: Rule out non-inflammatory causes. If non-inflammatory cause, treat accordingly and continue protocol therapy. Evaluate with imaging and pulmonary consultation as clinically appropriate.

Grade of Pneumonitis	Management	Follow-Up
Grade 1	
Consider delay of protocol therapy
 
Monitor for symptoms every 2-3 days
 
Consider Pulmonary and ID consults
	
Re-image at least every 3 weeks
 
If worsens:
 
Treat as Grade 2 or \geq Grade 3.

Grade 2	
Delay protocol therapy
 
Obtain Pulmonary and ID consults as clinically appropriate
 
Monitor symptoms daily, consider hospitalization
 
Administer 1.0 mg/kg/day methylprednisolone IV or oral equivalent
 
Consider bronchoscopy, lung biopsy as clinically appropriate
	
Re-image every 1-3 days
 
If improves:
 
When symptoms return to near baseline, taper steroids over at least 1 month and then resume protocol therapy and consider prophylactic antibiotics
 
If not improving after 2 weeks or worsening:
 
Treat as \geq Grade 3.

Table 6: Pulmonary Adverse Event Management

Note: Rule out non-inflammatory causes. If non-inflammatory cause, treat accordingly and continue protocol therapy. Evaluate with imaging and pulmonary consultation as clinically appropriate.

Grade of Pneumonitis	Management	Follow-Up
≥ Grade 3	
Permanently discontinue protocol therapy
 
Hospitalize as clinically indicated
 
Obtain pulmonary and ID consults as appropriate
 
Administer 2-4 mg/kg/day methylprednisolone IV or IV equivalent
 
Add prophylactic antibiotics for opportunistic infections
 
Consider bronchoscopy, lung biopsy
	
If improves to baseline: Taper steroids over at least 6 weeks.
 
If not improving after 48 hours or worsening: Add additional immunosuppression.

Patients on IV steroids may be switched to an equivalent dose of oral corticosteroids (e.g. prednisone) at start of tapering or earlier, once sustained clinical improvement is observed. Lower bioavailability of oral corticosteroids should be taken into account when switching to the equivalent dose of oral corticosteroids.

Table 7: Hepatic Adverse Event Management

Note: Rule out non-inflammatory causes. If non-inflammatory cause, treat accordingly and continue protocol therapy. Consider imaging for obstruction.

Grade of Liver Test Elevation	Management	Follow-Up
Grade 1	Continue protocol therapy	
Continue LFT monitoring per protocol
 
If worsens: Treat as Grade 2 or ≥ Grade 3.

Table 7: Hepatic Adverse Event Management

Note: Rule out non-inflammatory causes. If non-inflammatory cause, treat accordingly and continue protocol therapy. Consider imaging for obstruction.

Grade of Liver Test Elevation	Management	Follow-Up
Grade 2	
Delay protocol therapy
 
Increase frequency of monitoring to every 3 days
	
If returns to baseline:
 
Resume routine monitoring, resume protocol therapy
 
If elevations persist > 5-7 days or worsen:
 
Administer 0.5-1 mg/kg/day methylprednisolone or oral equivalent and when LFT returns to grade 1 or baseline, taper steroids over at least 1 month, consider prophylactic antibiotics for opportunistic infections, and resume protocol therapy

≥ Grade 3	
Permanently discontinue protocol therapy^A
 
Increase frequency of monitoring to every 1-2 days
 
Administer 1.0 to 2.0 mg/kg/day methylprednisolone IV or IV equivalent^B
 
Add prophylactic antibiotics for opportunistic infections
 
Consult gastroenterologist as clinically appropriate
	
If returns to grade 2:
 
Taper steroids over at least 1 month
 
If does not improve in >3-5 days, worsens or rebounds:
 
Add mycophenolate mofetil 1 g BID
 
If no response within an additional 3-5 days, consider other immunosuppressants per local guidelines

Patients on IV steroids may be switched to an equivalent dose of oral corticosteroids (e.g. prednisone) at start of tapering or earlier, once sustained clinical improvement is observed. Lower bioavailability of oral corticosteroids should be taken into account when switching to the equivalent dose of oral corticosteroids.
 
A. Protocol therapy may be delayed rather than discontinued if AST/ALT ≤ 8 × institutional ULN or total bilirubin ≤ 5 × institutional ULN.
 
B. The recommended starting dose for Grade 4 hepatitis is 2 mg/kg/day methylprednisolone IV.
		

Table 8: Endocrinopathy Adverse Event Management

Note: Rule out non-inflammatory causes. If non-inflammatory cause, treat accordingly and continue protocol therapy. Consider visual field testing, endocrinology consultation, and imaging.

Event	Management	Follow-Up
Asymptomatic TSH Elevation	
Continue protocol therapy.
 
If $TSH < 0.5 \times$ lower limit of normal (LLN), or $TSH > 2 \times$ ULN, or consistently out of range in 2 subsequent measurements: include free T4 at subsequent cycles as clinically indicated; consider endocrinology consult.
	
Symptomatic Endocrinopathy	
Evaluate endocrine function
 
Consider pituitary scan
 
Symptomatic with abnormal lab/pituitary scan:
 
Delay protocol therapy
 
Administer 1-2 mg/kg/day methylprednisolone IV or PO equivalent
 
Initiate appropriate hormone therapy
 
No abnormal lab/pituitary MRI scan but symptoms persist:
 
Repeat labs in 1-3 weeks / MRI in 1 month
	
If improves (with or without hormone replacement):
 
Taper steroids over at least 1 month and consider prophylactic antibiotics for opportunistic infections
 
Resume protocol therapy
 
Patients with adrenal insufficiency may need to continue steroids with mineralocorticoid component

Table 8: Endocrinopathy Adverse Event Management

Note: Rule out non-inflammatory causes. If non-inflammatory cause, treat accordingly and continue protocol therapy. Consider visual field testing, endocrinology consultation, and imaging.

Event	Management	Follow-Up
Suspicion of adrenal crisis (e.g. severe dehydration, hypotension, shock out of proportion to current illness)	
Permanently discontinue protocol therapy
 
Rule out sepsis
 
Stress dose of IV steroids with mineralocorticoid activity
 
Administer IV fluids
 
Consult endocrinologist as clinically appropriate
 
If adrenal crisis ruled out, then treat as above for symptomatic endocrinopathy
	

Patients on IV steroids may be switched to an equivalent dose of oral corticosteroids (e.g. prednisone) at start of tapering or earlier, once sustained clinical improvement is observed. Lower bioavailability of oral corticosteroids should be taken into account when switching to the equivalent dose of oral corticosteroids.

Table 9: Skin Adverse Event Management

Note: Rule out non-inflammatory causes. If non-inflammatory cause, treat accordingly and continue protocol therapy.

Grade of Rash^A	Management	Follow-Up
Grade 1 – 2	Continue protocol therapy. Administer symptomatic therapy (e.g. antihistamines, topical steroids)	If persists > 1-2 weeks or recurs: Consider skin biopsy Delay protocol therapy Consider 0.5-1.0 mg/kg/day methylprednisolone IV or oral equivalent. Once improving, taper steroids over at least 1 month, consider prophylactic antibiotics for opportunistic infections, and resume protocol therapy If worsens: Treat as Grade 3-4
Grade 3 – 4	Delay or discontinue protocol therapy Consider skin biopsy Dermatology consult as clinically appropriate Administer 1.0-2.0 mg/kg/day IV methylprednisolone IV or IV equivalent	If returns to Grade 1: Taper steroids over at least 1 month and add prophylactic antibiotics for opportunistic infections. Resume protocol therapy if appropriate.

Patients on IV steroids may be switched to an equivalent dose of oral corticosteroids (e.g. prednisone) at start of tapering or earlier, once sustained clinical improvement is observed. Lower bioavailability of oral corticosteroids should be taken into account when switching to the equivalent dose of oral corticosteroids.
 
A. If Stevens-Johnson Syndrome (SJS) or Toxic Epidermal Necrolysis (TEN) is suspected, withhold protocol therapy and refer patient for specialized care for assessment and treatment. If SJS or TEN is diagnosed, permanently discontinue protocol therapy.
		

Table 10: Neurological Adverse Event Management

Note: Rule out non-inflammatory causes. If non-inflammatory cause, treat accordingly and continue protocol therapy.

Grade of Neurological Toxicity	Management	Follow-Up
Grade 1	Continue protocol therapy.	Continue to monitor the patient. If worsens: Treat as Grade 2 or \geq Grade 3.
Grade 2	Delay protocol therapy Treat symptoms per local guidelines Consider 0.5 to 1.0 mg/kg/day methylprednisolone IV or oral equivalent	If improves to baseline: Resume protocol therapy. If worsens: Treat as \geq Grade 3.
\geq Grade 3	Permanently discontinue protocol therapy Obtain neurology consult as clinically appropriate Treat symptoms per local guidelines Administer 1.0-2.0 mg/kg/day methylprednisolone IV or IV equivalent Add prophylactic antibiotics for opportunistic infections	If returns to Grade 2: Taper steroids over at least 1 month. If worsens or atypical presentation: Consider IVIG or other immunosuppressive therapies per local guidelines.
Patients on IV steroids may be switched to an equivalent dose of oral corticosteroids (e.g. prednisone) at start of tapering or earlier, once sustained clinical improvement is observed. Lower bioavailability of oral corticosteroids should be taken into account when switching to the equivalent dose of oral corticosteroids.		

Table 11: Pancreatic Adverse Event Management

Note: Rule out non-inflammatory causes. If non-inflammatory cause, treat accordingly and continue protocol therapy.

Grade of Amylase or Lipase Elevation, Pancreatitis	Management^B	Follow-Up
Asymptomatic Grade 1 ^A	Continue protocol therapy. Monitor amylase and lipase weekly until resolution to baseline.	Resume routine protocol monitoring. If worsens: Treat as Grade 2-3 or 4.
Asymptomatic Grade 2-3 ^A	Delay protocol therapy. Monitor amylase and lipase weekly until resolution to baseline.	If improves to baseline: Resume protocol therapy and routine protocol monitoring. If worsens: Treat as Grade 4.
Asymptomatic Grade 4 ^A	Permanently discontinue protocol therapy. Monitor amylase and lipase weekly until resolution.	Monitor patient until resolution to baseline.
Any Symptomatic Elevations in Amylase/Lipase, Pancreatitis	Permanently discontinue protocol therapy. Consider GI consult as clinically appropriate. Administer supportive care.	Monitor patient until resolution to baseline.

- A. Patients should be monitored for signs/symptoms consistent with pancreatitis, including abdominal pain and vomiting.
- B. Corticosteroids do not seem to alter the natural course of amylase/lipase elevations.

Table 12: Ocular Adverse Event Management		
Note: Rule out non-inflammatory causes. If non-inflammatory cause, treat accordingly and continue protocol therapy. Work-up for ocular adverse events should also consider pituitary inflammation as a potential cause.		
Event Grade	Management^A	Follow-Up
Grade 1	
Continue protocol therapy.
 
Monitor patient for worsening symptoms.
 
Consider ophthalmologist consult as clinically appropriate.
 
Administer topical corticosteroids as clinically indicated.
	
If worsens:
 
Treat as Grade 2 or \geq Grade 3.

Grade 2	
Delay protocol therapy.
 
Obtain ophthalmologist consult.
 
Administer topical corticosteroids as clinically indicated.
	
If improves to baseline:
 
Resume protocol therapy.
 
If worsens:
 
Treat as \geq Grade 3.

\geq Grade 3	
Permanently discontinue protocol therapy.
 
Obtain ophthalmologist consult.
 
Administer systemic corticosteroids as clinically indicated.
	
Monitor patient until resolution to baseline.
 
Taper systemic corticosteroids as clinically appropriate.

Patients on IV steroids may be switched to an equivalent dose of oral corticosteroids (e.g. prednisone) at start of tapering or earlier, once sustained clinical improvement is observed. Lower bioavailability of oral corticosteroids should be taken into account when switching to the equivalent dose of oral corticosteroids.		

Table 13: Infusion-Related Reactions		
Event Grade	Management	Follow-Up
Grade 1	Monitor patient until recovery of symptoms to baseline.	Prophylactic premedications are recommended for future infusions: diphenhydramine 25 – 50 mg (or equivalent) and/or acetaminophen 325 to 1000 mg (or equivalent) at least 30 minutes before additional infusions.

Table 13: Infusion-Related Reactions

Event Grade	Management	Follow-Up
Grade 2	
Stop infusion.
 
Administer diphenhydramine 50 mg IV (or equivalent) and/or acetaminophen 325 – 1000 mg PO (or equivalent).
 
Corticosteroids or bronchodilators may also be administered as clinically appropriate.
 
Monitor patient until symptoms have resolved to baseline.
 
After resolution of symptoms, the infusion may be restarted at 50% of the original infusion rate. If no further complications ensue after 30 minutes, the rate may be increased to 100% of the original infusion rate. If symptoms recur, no further administration of nivolumab or ipilimumab should occur at that visit. Administer 50 mg IV diphenhydramine (or equivalent) and monitor patient until the symptoms resolve to baseline.
	
Prophylactic premedications are recommended for future infusions: diphenhydramine 50 mg (or equivalent) and/or acetaminophen 325 to 1000 mg (or equivalent), administered at least 30 minutes prior to the infusion.
 
If necessary per the judgment of the treating investigator, corticosteroids (up to 25 mg SoluCortef or equivalent) may be used as well.

≥ Grade 3	
Permanently discontinue protocol therapy.
 
Emergency care should be implemented as clinically appropriate and per local institutional standards of practice.
	
Monitor patient until resolution to baseline.

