3.1.4 ECOG performance status ≤ 1 (see **Appendix A**)

3.1.5 Participants must have normal organ and marrow function as defined below:

- Absolute neutrophil count $\geq 1,500/\text{mcL}$
- Platelets $\geq 100,000/\text{mcL}$
- Total bilirubin $\leq 1.5 \times$ institutional upper limit of normal (ULN)
- AST(SGOT)/ALT(SGPT) $\leq 2.5 \times$ institutional ULN, **OR**

- AST(SGOT)/ALT(SGPT) $\leq 5 \times$ institutional ULN if liver metastases are present
- Serum creatinine $\leq 1.5 \times$ institutional ULN, **OR**
- Creatinine clearance $\geq 60 \text{ mL/min}/1.73 \text{ m}^2$ for participants with serum creatinine levels above $1.5 \times$ institutional ULN.

3.1.6 Ability to understand and the willingness to sign a written informed consent document.

3.1.7 Participants must be able and willing to undergo a pre-treatment tumor tissue biopsy. Participants must also be willing to undergo an on-treatment tumor tissue biopsy if clinically feasible.

3.1.8 Participants must have a tumor tissue sample available (formalin-fixed paraffin embedded [FFPE] tissue block or unstained slides); may be newly obtained or obtained within 6 months prior to enrollment (without systemic therapy given after the sample was obtained). Participants without sufficient archival tissue may be enrolled following successful completion of the pre-treatment tumor tissue biopsy. Tissue must be a core needle biopsy, excisional, or incisional biopsy. Fine needle aspirates (FNA) or malignant effusions are not adequate. Bone biopsies without a soft tissue component are not adequate.

3.1.9 The effects of nivolumab and ipilimumab on the developing human fetus are unknown. For this reason, women of childbearing potential (WOCBP) must agree to follow instructions for acceptable contraception from the time of signing consent, and for 23 weeks after their last dose of protocol-indicated treatment. Should a woman become pregnant or suspect she is pregnant while she or her partner is participating in this study, she should inform her treating physician immediately. Men treated or enrolled on this protocol who are not azoospermic who are sexually active with WOCBP must agree to follow instructions for acceptable contraception from the time of signing consent, and for 31 weeks after their last dose of protocol-indicated treatment.

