5.5 Criteria for Taking a Participant Off Protocol Therapy

Duration of therapy will depend on individual response, evidence of disease progression and

tolerance. In the absence of treatment delays due to adverse event(s), treatment may continue for a maximum of 24 months or until one of the following criteria applies:

- Disease progression, unless the participant meets the requirements outlined in **Section 5.5.1**.
- Intercurrent illness that prevents further administration of treatment
- The patient becomes pregnant or plans to become pregnant
- Unacceptable adverse event(s)
- Participant decides to withdraw from the protocol therapy
- General or specific changes in the participant's condition render the participant unacceptable for further treatment in the judgment of the treating investigator

Participants will be removed from the protocol therapy when any of these criteria apply. The reason for removal from protocol therapy, and the date the participant was removed, must be documented in the case report form (CRF). Alternative care options will be discussed with the participant.

When a participant is removed from protocol therapy and/or is off of the study, the relevant Off-Treatment/Off-Study information will be updated in OnCore.

In the event of unusual or life-threatening complications, treating investigators must immediately notify the Overall PI, [name] at [contact].

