6.2 Dose Delays

Dosing of ipilimumab or nivolumab may be held at the treating investigator's discretion for any toxicity of any grade. Additionally, holding of the study agents may be required as indicated in the tables in **Section 6.1**.

A treatment delay of up to six weeks for nivolumab and up to 12 weeks for ipilimumab is allowable. Participants requiring a longer hold should be removed from protocol therapy. Exceptions for participants exhibiting clinical benefit may be possible with approval from the principal investigator.

If study agent dosing is held due to toxicity, the counting of cycle days and assessment schedule will continue without interruption. For example, a participant who does not receive their Cycle 3

Day 15 dose of nivolumab due to toxicity will proceed with their next regularly scheduled clinic visit (Cycle 3 Day 29) as previously planned. Additional interim clinic visits may be scheduled to manage toxicity, however the cycle will not restart due to dosing delays due to adverse events and the assessment schedule (including tumor imaging evaluations) will continue as originally planned.

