6.3 Dose Reductions

There will be no dose reductions for nivolumab or ipilimumab allowed. Participants who cannot tolerate the assigned doses of nivolumab or ipilimumab should be removed from protocol therapy.

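### Table 7 footnote A joins its two liver limits with *or*, so read literally an isolated AST/ALT or bilirubin rise of any size escapes mandatory permanent discontinuation

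*Combined protocol and SAP*

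**What the plan says.** In Section 6.1, Table 7, the row for Grade 3 or higher instructs "Permanently discontinue protocol therapy^A". The superscript leads to footnote A: "Protocol therapy may be delayed rather than discontinued if AST/ALT ≤ 8 × institutional ULN or total bilirubin ≤ 5 × institutional ULN". Footnote B, attached to the same row, shows that the row includes Grade 4: "The recommended starting dose for Grade 4 hepatitis is 2 mg/kg/day methylprednisolone IV".

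The Grade 2 row states when treatment may restart once steroids have been used: "when LFT returns to grade 1 or baseline, taper steroids over at least 1 month", followed by resumption. The follow-up cell for Grade 3 or higher says when to begin tapering steroids (return to Grade 2) and when to add further immunosuppression. It says nothing about resuming after a delay taken under footnote A.

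Three other sections bear on the point:

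- **Section 3.1.5** sets the entry limits: bilirubin up to 1.5 × ULN, and AST/ALT up to 2.5 × ULN, or 5 × ULN with liver metastases.
- **Section 6.2** limits the length of a hold: "A treatment delay of up to six weeks for nivolumab and up to 12 weeks for ipilimumab is allowable".
- **Section 6.3** states "There will be no dose reductions for nivolumab or ipilimumab allowed".

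**The concern.** The footnote is an exception to a patient-safety stopping rule. Its two thresholds look like ceilings above which delay is no longer acceptable. Joined by *or*, they do not act as ceilings, because a normal value on one test satisfies the condition for both. A participant with an extreme isolated transaminase or bilirubin rise could be held and later rechallenged within the letter of the protocol. With dose reductions barred, whichever drug is restarted is restarted at its full dose.

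Liver toxicity is a known risk of this combination. Section 2.4.4 lists autoimmune hepatitis among the drug-related serious events in the newer combination cohorts. It also lists raised ALT, raised AST and autoimmune hepatitis among the events that led to discontinuation.

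Most of the other toxicity tables have no comparable exception. Gastrointestinal, pulmonary, neurological and ocular events of Grade 3 or higher, Grade 4 creatinine elevation and asymptomatic Grade 4 amylase or lipase elevation all require permanent discontinuation. Skin (Table 9) allows delay or discontinuation, but requires permanent discontinuation for diagnosed Stevens-Johnson syndrome or toxic epidermal necrolysis.

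**Working it through.** No sample-size or error-rate figure is involved. The check applies the rule as written to pairs of values and then looks for any other provision that would close the gap.

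**Rule.** Let A be AST/ALT and B total bilirubin, both in multiples of ULN, for a participant already in the row for Grade 3 or higher.

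- As written, delay is permitted if A ≤ 8 or B ≤ 5. Discontinuation is compulsory only if A > 8 and B > 5.
- With *and*, delay is permitted if A ≤ 8 and B ≤ 5. Discontinuation is compulsory if A > 8 or B > 5.

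**Starting point.** At entry B ≤ 1.5 and A ≤ 2.5 (or ≤ 5 with liver metastases). Since 1.5 < 5 and 5 < 8, anyone meeting Section 3.1.5 starts inside both limits.

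**Cases.** The values 1.5 and 2.5 are entry limits; 8 and 5 are the footnote limits; all other values are illustrative.

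| A (× ULN) | B (× ULN) | As written (*or*) | With *and* |
|---|---|---|---|
| 6 | 1.5 | may delay | may delay |
| 8 | 5 | may delay | may delay |
| 20 | 1.5 | may delay | must discontinue |
| 50 | 1 | may delay | must discontinue |
| 2.5 | 12 | may delay | must discontinue |
| 30 | 4.9 | may delay | must discontinue |
| 7.9 | 15 | may delay | must discontinue |
| 10 | 6 | must discontinue | must discontinue |

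Each test is either within or above its limit, giving 2 × 2 = 4 combinations. Under *or*, one of the four forces discontinuation; under *and*, three do. This counts logical cells and does not estimate how often they occur. The rows (30, 4.9) and (7.9, 15) show that the gap is not confined to isolated rises: both tests may be well above normal, provided one stays within its limit.

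**Search for a backstop.**

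- Footnote B sets a steroid starting dose for Grade 4 and does not restore compulsory discontinuation.
- Section 5.5 removes participants for unacceptable adverse events, with no liver threshold.
- Section 6.2 limits how long a hold may last, not how high the test may go, and the principal investigator may grant exceptions for clinical benefit.
- Section 6.3 removes participants who cannot tolerate the assigned doses, again with no liver threshold.
- Section 7.2.4 (potential drug-induced liver injury) requires both AT above 3 × ULN and bilirubin above 2 × ULN, and its consequence is SAE reporting.
- Section 2.2.6 says that ipilimumab should in general be stopped for severe inflammatory events. That is background text about one of the two drugs.

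None of these forces discontinuation for an isolated rise above 8 × or 5 × ULN.

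**The case against.** The strongest reply is that a clinician would read the footnote test by test: the 8 × limit applies if AST/ALT put the participant in the row, and the 5 × limit if bilirubin did. On that reading an isolated rise is judged against its own limit and the gap disappears. This is plausible and is probably what was meant. The text does not say it, however, and Section 7.2.4 joins its liver criteria with a capitalised AND, so readers have reason to take these conjunctions literally. If the test-by-test reading is intended, changing the word costs nothing.

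Several further points narrow the practical consequence:

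- The footnote is permissive, discontinuation stays the default, and the row's monitoring, steroid, antibiotic and consultation instructions still apply. An investigator would have to choose to rechallenge.
- The six-week nivolumab hold is 42 days. Taking one month as 30 days, a completed taper leaves 42 − 30 = 12 days for the test to fall far enough to start tapering (11 to 14 days if a month is 31 to 28 days). Slow-resolving cases would often come off nivolumab anyway, unless an exception is granted.
- Section 6.2 sets separate limits for the two drugs, so rechallenge with both does not necessarily follow.
- Section 5.2.1 allows discussed exceptions to re-meeting laboratory criteria on Cycle 1 Day 1, so a few participants could start treatment outside the entry limits.
- If the table is read by current grade, someone who improves to Grade 2 falls under the Grade 2 row and its resumption criterion. That makes the missing resumption rule less serious than the conjunction.

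These points limit how often harm could follow. They do not put an upper limit on the exception.

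**Conclusion.** The concern holds. As worded, footnote A forces permanent discontinuation only when AST/ALT is above 8 × ULN and bilirubin is above 5 × ULN together, and no other section supplies the missing ceiling. The conclusion rests on the literal wording; the logic is certain, while the intended meaning is inferred. The number of participants affected cannot be derived from the documents, and no endpoint, sample size or analysis is touched. The conjunction is the main defect. The absent resumption criterion is secondary and closer to missing detail. The correction should be made, because a safety stopping threshold should not depend on each reader mentally repairing its wording.

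**What to change.** In footnote A, insert *only* before *if* and replace *or* with *and*, so that delay is available only when AST/ALT is at or below 8 × ULN and bilirubin is at or below 5 × ULN.

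In the follow-up cell for Grade 3 or higher, add one sentence: after a delay under footnote A, treatment restarts only once liver tests are back to Grade 1 or baseline and the steroid taper of at least one month is complete, within the hold limits of Section 6.2. This reuses the Grade 2 criterion. It can fit within six weeks for nivolumab if recovery is prompt.

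If the sponsor does intend an isolated rise of any size to be eligible for delay, the protocol should say so and give the reason.

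The cost is a two-word edit to a footnote and one sentence in a table cell. No patients, visits, tests or analyses are added.
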